6.5.3.4. Infusion rate reductions

Applicable to avelumab.

The number and percentage of patients with at least one infusion rate reduction of $\geq 50\%$ compared to the first infusion rate reported in the eCRF as well as the frequency of patients with 1, 2, 3, or ≥ 4 infusion rate reductions of $\geq 50\%$ will be summarized for Arm A.

6.5.3.5. Infusion interruptions

Applicable to avelumab.

An infusion interruption is defined as an infusion that is stopped and re-started on the same day (ie, for a visit more than one infusion start time and infusion end time are recorded).

The number and percentage of patients with at least one infusion interruption as well as the frequency of patients with 1, 2, 3, or ≥ 4 infusion interruptions will be summarized for Arm A.

6.5.3.6. Duration of BSC

The duration of BSC (in weeks) during the study for a patient is defined as:

$$\text{Treatment duration (weeks)} = (\text{end date of BSC} - \text{start date of BSC} + 1)/7$$

where end and start dates of BSC are defined in [Section 3.4.1](#).

6.5.4. Concomitant medications and non-drug treatments

The following analyses will be based on the safety analysis set by treatment arm.

Concomitant medications are medications, other than study drugs, which started prior to first dose date of study treatment and continued during the on-treatment period as well as those started during the on-treatment period. **Prior medications** are medications, other than study drugs and pre-medications for study drug, which are started before the first dose of study treatment.

Prior and concomitant medications will be summarized from the ‘General Concomitant Medications’ eCRF page. Pre-medications for study drug will also be summarized separately from the ‘Pre-Medication Treatment’ eCRF page.

Summary of prior medications, summary of concomitant medications and summary of pre-medications will include the number and percentage of patients by Anatomical Therapeutic Chemical (ATC) Classification level 2 and preferred term. A patient will be counted only once within a given drug class and within a given drug name, even if he/she received the same medication at different times. If any prior or concomitant medication is classified into multiple ATC classes, the medication will be summarized separately under each of these ATC classes. The summary tables will be sorted on decreasing frequency of drug class and decreasing frequency of drug name in a given drug class. In case of equal frequency regarding drug class (respectively drug name), alphabetical order will be used. In case any specific medication does not have ATC classification level 2 coded term, it will be summarized under ‘Unavailable ATC classification’ category.

A listing of prior medications and a listing of concomitant medications will be created with the relevant information collected on the ‘General Concomitant Medications’ eCRF page. A listing of pre-medications will be created with the relevant information collected on the ‘Pre-Medication Treatment’ eCRF page.

All concurrent procedures, which were undertaken any time during the on-treatment period, will be listed according to the eCRF page ‘General Non-drug Treatments’.

A listing of concurrent procedures will be created with the relevant information collected on the ‘General Non-drug Treatments’ eCRF page.

6.5.5. Subsequent anti-cancer therapies

The following analyses will be based on the FAS by treatment arm.

Anti-cancer treatment will be provided in a data listing with data retrieved from ‘Follow-up Cancer Therapy’, ‘Concomitant Radiation Therapy’, ‘Follow-up Radiation Therapy’, ‘Concomitant Surgery’, and ‘Follow-up Surgery’ eCRF pages.

Number and percentage of patients with any anti-cancer therapy after discontinuation will be tabulated overall and by type of therapy based on the data collected from the ‘Follow-up Cancer Therapy’, ‘Follow-up Radiation Therapy’ and ‘Follow-up Surgery’ eCRF pages. The number and percentage of patients with anti-cancer drug therapies based on the data collected from the ‘Follow-up Cancer Therapy’ will also be summarized for patients with PD-L1-positive tumors, by treatment arm.

6.6. Safety Summaries and Analyses

The Safety Analysis Set will be the primary population for safety evaluations. Summaries of AEs and other safety parameters will be based on the safety analysis set by treatment arm.

6.6.1. Adverse events

Treatment-emergent adverse events (TEAEs) are those events with onset dates occurring during the on-treatment period as defined in [Section 3.5.1](#).

All analyses described below will be based on TEAEs (started during the on-treatment period) if not otherwise specified. The AE listings will include all AEs (whether treatment-emergent or not). AEs with onset outside the on-treatment period will be flagged in the listings.

- **Related Adverse Events:** adverse events with relationship to study treatment (as recorded on the AE eCRF page, Relationship with study treatment = Related) reported by the investigator and those of unknown relationship (ie, no answer to the question ‘Relationship with study treatment’).
- **Serious Adverse Events (SAE):** serious adverse events (as recorded on the AE eCRF page, Serious Adverse Event = Yes).
- **Adverse Events Leading to Dose Reduction:** adverse events leading to dose reduction of study treatment (as recorded on the AE eCRF page, Action taken with study treatment = Dose reduced).
- **Adverse Events Leading to Interruption of Study Treatment:** adverse events leading to interruption of study treatment (as recorded on the AE eCRF page, Action taken with study treatment = Drug interrupted). The eCRF does not allow for a clear separation between interruption of an infusion and delays of administration for a parenteral drug, as both are recorded using the same term on the eCRF (“Drug interrupted”). IRRs will be excluded in the analysis of AEs leading to Drug Interruption in case they only led to an interruption of the infusion.

- **Adverse Events Leading to Permanent Treatment Discontinuation:** adverse events leading to permanent discontinuation of study treatment (as recorded on the AE eCRF page, Action taken with study treatment = Drug withdrawn).
- **Adverse Events Leading to Death:** adverse event leading to death (as recorded on the AE eCRF page, Outcome = Fatal, as well as AEs of Grade 5).
- **Immune-related Adverse Events (irAE):** irAEs (as identified according to the methodology outlined in [Appendix 1](#) for a pre-specified search list of MedDRA PTs, documented in the Safety Review Plan [SRP] and finalized for analysis of the current studies data prior to DB lock)
- **Infusion-related Reactions (IRR):** IRRs (as identified according to the methodology outlined in [Appendix 2](#) for a pre-specified search list of MedDRA PTs documented in the SRP and finalized for analysis of the current studies data prior to DB lock).

Unless otherwise specified, AEs will be summarized by number and percentage of patients with the AE in the category of interest as described above, by treatment arm, primary SOC and PT in decreasing frequency based on the frequencies observed for Arm A.

Each patient will be counted only once within each SOC or PT. If a patient experiences more than one AE within a SOC or PT for the same summary period, only the AE with the strongest relationship or the worst severity, as appropriate, will be included in the summaries of relationship and severity.

6.6.1.1. All Adverse Events

Adverse events will be recorded on the 'Adverse Event' eCRF page. Action taken with BSC for patients in Arm A will not be summarized.

Adverse events will be summarized by worst severity (according to NCI-CTCAE version 4.03) per patient, using the latest version of MedDRA preferred term (PT) as event category and MedDRA primary system organ class (SOC) body term as Body System category.

In case a patient has events with missing and non-missing grades, the maximum of the non-missing grades will be displayed. No imputation of missing grades will be performed.

The following tables will be created:

- The overall summary of AEs table will include the frequency (number and percentage) of patients with each of the following by treatment arm:
 - TEAEs
 - TEAEs, Grade ≥ 3
 - Related TEAEs
 - Related TEAEs, Grade ≥ 3
 - TEAEs leading to dose reduction of avelumab

- TEAEs leading to interruption of avelumab
 - TEAEs leading to discontinuation of avelumab
 - TEAEs leading to discontinuation of BSC
 - Related TEAEs leading to discontinuation of avelumab
 - Related TEAEs leading to discontinuation of BSC
 - Serious TEAEs
 - Related Serious TEAEs
 - TEAEs leading to death
 - Related TEAEs leading to death
 - irAEs
 - IRRs
- TEAEs by SOC and PT and worst grade
 - Related TEAEs by SOC and PT and worst grade
 - TEAEs leading to death by SOC and PT
 - Related TEAEs leading to death by SOC and PT
 - TEAEs Excluding SAEs, with frequency $\geq 5\%$ in any treatment arm by SOC and PT

6.6.1.2. Adverse events leading to dose reduction

Applicable to Arm A only.

The frequency (number and percentage) of patients with each of the following will be presented for TEAEs leading to dose reduction of avelumab for Arm A:

- TEAEs leading to dose reduction of avelumab by SOC and PT

The listing of all AEs leading to dose reduction will also be provided with the relevant information.

6.6.1.3. Adverse events leading to interruption of study treatment

Applicable to Arm A only.

The eCRF does not allow for a clear separation between interruption of an infusion and delays of administration for a parenteral drug as both are recorded using the same term on the eCRF (“Drug interrupted”). IRRs will be excluded in the analysis of AEs leading to Drug Interruption in case they only led to an interruption of the infusion (ie, did not lead to a dose reduction or a dose delay).

As such, AEs leading to interruption will be defined as AEs identified in the AE eCRF page with an action taken with study treatment of ‘drug interrupted’ excluding

- IRRs that occurred on the day of infusion with $\geq 90\%$ of the planned dose given (ie IRRs that did not lead to a dose reduction) and subsequent administration of study drug had no delay (as defined in Section 6.5.3.3). These IRRs will be considered as IRRs leading to interruption of infusion.
- IRRs occurring on the day after infusion and subsequent dose administration had no delay (as defined in Section 6.5.3.3).

The frequency (number and percentage) of patients with each of the following will be presented for TEAEs leading to interruption of avelumab for Arm A:

- TEAEs leading to interruption of avelumab by SOC and PT

The listing of all AEs leading to interruption of study treatment will also be provided with the relevant information.

In addition, the frequency (number and percentage) of patients with each of the following will be presented for TEAEs leading to interruption of avelumab for Arm A:

- TEAEs leading to both interruption and dose reduction of avelumab by SOC and PT

This summary will take into account PTs with both actions as defined in Section 6.6.1, even though the actions may be captured for different PT records (ie, different onset for the PT with action “drug interrupted” and the PT with action “dose reduced”).

6.6.1.4. Adverse Events Leading to Treatment Discontinuation

The frequency (number and percentage) of patients with each of the following will be presented for TEAEs leading to permanent discontinuation of each study drug and study treatment, by treatment arm:

- TEAEs leading to discontinuation of avelumab by SOC and PT
- Related TEAEs leading to discontinuation of avelumab by SOC and PT
- TEAEs leading to discontinuation of BSC by SOC and PT
- Related TEAEs leading to discontinuation of BSC by SOC and PT

The listing of all AEs leading to treatment discontinuation will also be provided with the relevant information.

6.6.2. Deaths

The frequency (number and percentage) of patients in the safety analysis set who died and who died within 30 days after last dose of study treatment as well as the reason for death will be tabulated based on information from the ‘Notice of Death’ and ‘Survival Follow-Up’ eCRFs, by treatment arm.

- All deaths
- Deaths within 30 days after last dose of study treatment
- Reason for Death
 - Disease progression
 - Study treatment toxicity
 - AE not related to study treatment
 - Unknown
 - Other.

In addition, date and cause of death will be provided in individual patient data listing together with selected dosing information (study treatment received, date of first / last administration, dose) and will include the following information:

- AEs with fatal outcome (list preferred terms of AEs with outcome = Fatal, as well as AEs of Grade 5),
- Flag for death within 30 days of last dose of study treatment.

6.6.3. Serious adverse events

The frequency (number and percentage) of patients with each of the following will be presented for treatment-emergent SAEs by treatment arm:

- SAEs by SOC and PT
- Related SAEs by SOC and PT

The listings of all SAEs will also be provided with the relevant information with a flag for SAEs with onset outside of the on-treatment period.

6.6.4. Other significant adverse events

The frequency (number and percentage) of patients with each of the following will be presented for irAEs, by treatment arm:

- irAEs leading to death, by Cluster and PT
- irAEs, by Cluster and PT
- irAEs, Grade ≥ 3 , by Cluster and PT
- irAEs leading to discontinuation of avelumab, by Cluster and PT
- irAEs leading to discontinuation of BSC, by Cluster and PT
- Serious irAEs, by Cluster and PT

The listing of all irAEs will also be provided with the relevant information with a flag for irAEs with onset outside of the on-treatment period.

The frequency (number and percentage) of patients with each of the following will be presented for IRRs, by treatment arm:

- IRRs leading to death, by PT
- IRRs, by PT
- IRRs, Grade ≥ 3 , by PT
- IRRs leading to discontinuation of avelumab, by PT
- Serious IRRs, by PT
- Time related to first onset of an IRR (infusion 1, infusion 2, infusion 3, infusion 4 or later).

The listing of all IRRs will also be provided with the relevant information with a flag for IRRs with onset outside of the on-treatment period.

In addition, the following analyses will be presented for irAEs (as defined in [Appendix 1](#)) and Tier-2 events separately. CIs for risk difference will be calculated based on the unconditional exact method by [Santner and Snell \(1980\)](#). No additional analyses will be presented for Tier-3 AEs.

- Frequency (number and percentage) of patients with each of the following by treatment arm and PT or Clustered Term:
 - Tier-2 AEs
 - Tier-2 AEs Grade ≥ 3
- Point estimate for risk difference and 95% CI for risk difference (experimental arm vs comparator arm) for each of the following by PT or Clustered Term:
 - irAEs
 - irAEs Grade ≥ 3
 - Tier-2 AEs
 - Tier-2 AEs Grade ≥ 3
- CIs reported are not adjusted for multiplicity and should be used for screening purposes only. The 95% CIs are provided to help gauge the precision of the estimates for the risk difference and should be used for estimation purposes only.

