3.5. Safety Endpoints

3.5.1. Adverse events

Treatment-Emergent Adverse Events

Treatment-emergent adverse events (TEAEs) are those events with onset dates occurring during the on-treatment period.

On-treatment period is defined as follows:

- Arm A: time from the first dose of study treatment through minimum (30 days + last dose of study treatment, start day of new anti-cancer drug therapy – 1 day)
- Arm B: time from Cycle 1 Day 1 through minimum (30 days + end date of BSC, start day of new anti-cancer drug therapy – 1 day).

As defined in [Section 3.4.1](#), ‘End date of BSC’ is the date of completion or discontinuation as collected in the ‘Disposition - Treatment Phase’ eCRF page.

The start day of new anti-cancer drug therapy after the first dose of study treatment is derived as outlined in [Section 5.2.5](#).

Adverse Events of Special Interest (AESIs)

AESIs are immune-related adverse events (irAE) and infusion-related reactions (IRRs). The criteria for classification of an AE as an irAE or IRR are described in [Appendix 1](#) and [Appendix 2](#), respectively.

3-Tier Adverse Events

It should be recognized that most studies are not designed to reliably demonstrate a causal relationship between the use of a pharmaceutical product and an adverse event or a group of adverse events. Except for select events in unique situations, studies do not employ formal adjudication procedures for the purpose of event classification. As such, safety analyses are generally considered as an exploratory analysis and its purpose is to generate hypotheses for further investigation. The 3-tier approach facilitates these exploratory analyses.

Adverse events and clusters of adverse events, of any causality and treatment-related, will also be summarized following a 3-tier approach. Under this approach, AEs are classified into 1 of 3 tiers.

Tier-1 events: These are pre-specified events or clusters of events of clinical importance and will be described in the Safety Review Plan.

Tier-2 events: These are events that are not Tier-1 but are “common”. A MedDRA PT is defined as a Tier-2 event if it is reported by

- a) at least 10% of patients with any grade in any treatment arm, or
- b) at least 5% of patients with Grade 3, 4 or 5 in any treatment arm.

Tier-3 events: All other AEs that are classified neither as Tier-1 nor Tier-2.

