4.2. Safety Analysis Set

The safety analysis set will include all patients who receive at least one dose of study drug on Arm A or completed C1D1 on Arm B. If a patient randomized to Arm B incorrectly receives avelumab, then the patient will be classified in Arm A for the purpose of safety analyses.

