5. GENERAL METHODOLOGY AND CONVENTIONS

5.1. Hypotheses and Decision Rules

5.1.1. Hypotheses and sample size determination

The study is designed to test, in parallel, the following hypotheses:

$$H_{0 \text{ All patients}}: HR_{OS (Arm A/Arm B)} \geq 1, \text{ versus } H_{a \text{ All patients}}: HR_{OS (Arm A/Arm B)} < 1$$

$$H_{0 \text{ PD-L1+}}: HR_{OS (Arm A/Arm B)} \geq 1, \text{ versus } H_{a \text{ PD-L1+}}: HR_{OS (Arm A/Arm B)} < 1$$

where HR_{OS} represents the hazard ratio for OS in the experimental arm vs the control arm.

Approximately 668 patients will be randomized to the treatment arms using a 1:1 randomization, stratified by best response to chemotherapy (CR or PR vs. SD) and site of metastasis (visceral vs. non-visceral) at time of initiating first-line chemotherapy. The type 1 error rate will be split between the co-primary populations to preserve the overall type 1 error rate for the study at 0.025 one-sided. It is estimated that at least 50% of the randomized patients will have adequate tissue for analysis and be determined to have PD-L1-positive tumors.

The sample size for this study is determined based on the following assumptions:

- For all patients and patients with PD-L1-positive tumors receiving BSC alone after first-line chemotherapy, the median OS is 12 months (Powles et al, 2015).
- For all patients receiving avelumab + BSC after first-line chemotherapy, the median OS is assumed to be 17.1 months.

- For patients with PD-L1-positive tumors receiving avelumab + BSC after first-line chemotherapy, the median OS is assumed to be 18.5 months.

This corresponds to a hazard ratio (HR) of 0.7 for all patients and 0.65 for patients with PD-L1-positive tumors under the exponential model assumption.

For all patients, if the true HR is 0.7 under the alternative hypothesis, a total of 425 OS events will be required to have 93% power to detect a HR of 0.7 using a one-sided log rank test at a significance level of 0.015 and a 2-look group-sequential design with Lan-DeMets (O'Brien-Fleming) α -spending function to determine the efficacy boundary and a Gamma Family (-8) β -spending function to determine the non-binding futility boundary.

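### For rare adverse events, the exact interval cited in SAP 6.6.4 is, in its raw-difference form, about 2.7 to 4 times as wide as a score interval and gauges precision poorly

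*SAP*

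**What the plan says.** SAP Section 6.6.4 lists "Point estimate for risk difference and 95% CI for risk difference (experimental arm vs comparator arm"), by preferred term or clustered term, for four sets of events: irAEs, irAEs of Grade ≥3, Tier-2 AEs and Tier-2 AEs of Grade ≥3. On method it says "CIs for risk difference will be calculated based on the unconditional exact method by" Santner and Snell, citing a 1980 paper. No ordering statistic or software option is given.

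The same section limits how the intervals are to be used: "CIs reported are not adjusted for multiplicity and should be used for screening purposes only". It also gives them a purpose: "The 95% CIs are provided to help gauge the precision of the estimates for the risk difference". There is no rule that an interval covering zero means no difference.

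A Tier-2 event (SAP 3.5.1) is one that reaches 10% in either arm at any grade, or "at least 5% of patients with Grade 3, 4 or 5 in any treatment arm". The change table in SAP Section 1 records that nominal p-values for Tier-1 risk differences were dropped. SAP Appendix 1 draws irAEs from the Tier-1 list. For irAEs, these intervals are therefore the only between-arm measure of uncertainty planned.

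**The concern.** An unconditional exact interval has to deal with the unknown background rate. If tables are ordered by the raw difference in proportions, and the tail probability is maximised over that rate, the maximum falls near a rate of 50%, where a difference in proportions varies most. The interval then carries the width appropriate to a 50% event even when only a few patients per arm are affected.

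Many rows in these tables will concern rare events. Protocol Section 1.2.2.1 reports treatment-related irAEs in 717 avelumab patients: hypothyroidism in 4.5%, pneumonitis in 1.1%, autoimmune hepatitis in 0.6% and colitis in 0.4%. An interval whose width does not respond to the event rate says little about how precisely such a difference has been estimated, and it is a weak screen.

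**Working it through.** **Inputs**
- Arm size: "Approximately 668 patients will be randomized to the treatment arms using a 1:1 randomization" (SAP 5.1.1), so 668 / 2 = 334 per arm. The safety set counts treated patients (SAP 4.2: "The safety analysis set will include all patients who receive at least one dose of study drug on Arm A", or who completed Cycle 1 Day 1 on Arm B). The treated number is not stated, so 334 is an assumption; 300 to 350 was also checked.
- Level: 95% two-sided, 0.025 per tail.
- Ordering: raw difference, unstandardised. This is also an assumption, because the SAP cites the method without giving the statistic.

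The documents state no interval width or detectable AE difference, so there is no plan figure to reproduce.

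**Formula.** With observed difference d = x1/n − x2/n, the lower limit is the value Δ at which

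max over p of P( X1/n − X2/n ≥ d | rates p + Δ and p ) = 0.025,

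and the upper limit is found in the same way from the other tail.

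**Why the half-width is about 7.7 points.** At p = 0.5 the standard error is √(2 × 0.25 / 334) = 0.0387. Then 1.96 × 0.0387 = 0.0758, or 7.6 points. Half a lattice step, 0.5 / 334 = 0.15 points, brings this to about 7.7. Exact computation gives 7.72 at 0 vs 0, 17 vs 17, 33 vs 33 and 167 vs 167. It narrows only for very large differences: 100 vs 5 gives 7.53 below the estimate and 7.28 above.

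**Comparison at 334 per arm (percentage points)**

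| Events | Raw-difference exact | Score-based | Width ratio |
|---|---|---|---|
| 10 vs 0 | -4.73 to 10.70 | 1.6 to 5.4 (Miettinen-Nurminen) | 15.43 / 3.8 = 4.1 |
| 17 vs 0 | -2.64 to 12.78 | 2.99 to 8.02 (exact score) | 15.42 / 5.03 = 3.1 |
| 25 vs 0 | -0.25 to 15.15 | 5.1 to 10.8 (Miettinen-Nurminen) | 15.40 / 5.7 = 2.7 |
| 33 vs 33 | -7.72 to 7.72 | -4.67 to 4.67 (exact score) | 15.44 / 9.34 = 1.7 |
| 100 vs 100 | -7.72 to 7.72 | Miettinen-Nurminen | 1.1 |

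Below 10 events the ratio is larger still. At 5 vs 0 the raw interval is -6.23 to 9.21 and the exact score interval 0.26 to 3.50, so 15.44 / 3.24 = 4.8.

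**Where zero is first excluded.** The worst-case one-sided p at Δ = 0 is 0.0290 for 25 vs 0 and 0.0242 for 26 vs 0, both at p = 0.5. So 26 vs 0 is the first split to exclude zero (25 at 300 per arm, 27 at 350). For contrast, Fisher's two-sided p is 0.0018 for 10 vs 0 and 3.7 × 10⁻⁸ for 25 vs 0.

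**Against the plan's own rates.** A Grade ≥3 Tier-2 event at its 5% entry threshold is about 17 of 334, and 17 vs 0 covers zero. Hypothyroidism at 4.5%, with none assumed on BSC, is about 15 vs 0 and gives -3.24 to 12.18.

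**Against the sampling variation.** With true rates of 5% and 1%, the standard deviation of the difference is √((0.05 × 0.95 + 0.01 × 0.99) / 334) = 1.31 points. The half-width is then 7.72 / 1.31 = 5.9 standard deviations, where about 1.96 would be expected. Zero would be excluded in 0.4% of trials, against 90% for a pooled score test.

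**The case against.** The main objection is to the premise. The SAP names a method by citation only, and an exact unconditional interval can also be built on a standardised statistic, which would not behave this way. That stands as a condition on every figure above. It does not remove the point, because the text names no such variant and the remedy is to name one.

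A reader might infer that real immune toxicity would be hidden, or that 25 vs 0 would be reported as no difference. The documents do not support that. SAP 6.6.4 ties no decision to an interval covering zero and restricts the intervals to screening and estimation. It also tabulates irAEs by arm, cluster and term (any grade, Grade ≥3, serious, fatal and leading to discontinuation), with point estimates and listings. A split of 25 vs 0 would be visible as 7.5% vs 0%.

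A reader might also infer that all four tables are several times too wide. They are not. For events near 10% incidence the ratio is about 1.7, at 20% (67 vs 67) 1.27, and at 30% about 1.1. Pooled irAE counts are also less affected: a split such as 50 vs 3 gives 6.4 to 21.7 and clearly excludes zero.

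Finally, these are exploratory, unadjusted safety summaries, and guaranteed coverage is a legitimate aim. That is fair, but an exact interval based on the score statistic keeps the guarantee without the excess width.

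**Conclusion.** The point holds for rare events, meaning individual irAE terms and the Grade ≥3 tables. There the interval is about 2.7 to 4 times as wide as a score interval for splits between 25 vs 0 and 10 vs 0, and its width hardly changes with the event rate. It therefore does not serve the screening and precision purpose that SAP 6.6.4 gives it. For common Tier-2 events the cost is modest.

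Two assumptions carry the result: that the cited method is used in its raw-difference form, and that about 334 patients per arm are treated. The first is decisive; the second moves the zero-exclusion threshold only between 25 and 27 events against none. This concerns the quality of safety reporting. It does not touch the OS analysis, the type I error or any efficacy endpoint.

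**What to change.** In SAP 6.6.4, name the interval in full for all four risk-difference tables. Use either the unconditional exact interval based on the score statistic (Chan-Zhang; METHOD=SCORE in the RISKDIFF option of SAS PROC FREQ) or the Miettinen-Nurminen score interval. If a score-based version was always intended, the same sentence settles it.

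With the exact score version, 17 vs 0 gives 2.99 to 8.02 and 25 vs 0 gives 4.90 to 10.86, and zero is excluded from 4 vs 0 upward (worst-case one-sided p = 0.0242).

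The cost is one sentence and one procedure option, with no new data. Miettinen-Nurminen does not guarantee exact coverage. The exact score version does, at slightly more computation.
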